## Statistical Analysis Plan

Preliminary Analyses. In initial analyses, we will summarize categorical variables by proportions and continuous variables by means and quantiles. We will graph continuous variables and assess them for skewness, transforming if necessary (for example by logs or square roots) to render them more nearly normally distributed. We will explore relationships among variables by examining scatter plots and correlation matrices. We will conduct all analyses in R (version 3.3.2 or later) or SAS (version 9.4 or later).

Analysis of Primary Outcome Variables. The primary cognitive outcome endpoint will be a composite, scalar episodic memory score, as described in earlier research from the SYNAPSE project (5). This measure will exhibit substantial between-subject variability, in that subjects who give high scores at baseline are likely to give high scores at follow-up as well. To account for this, in primary analyses we will adjust for baseline levels by analysis of covariance — i.e., including baseline values together with treatment arm in a regression model for the post-treatment outcome. Alternatively (and equivalently), we can analyze the outcome variable in a mixed model, evaluating a treatment effect by estimating a time-by-treatment interaction. We will moreover conduct mixed-model analyses including the intermediate (6-week, mid-treatment) and long-term (1-year) values of the cognitive outcomes together with the end-of-treatment (12-week) outcome. As a secondary analysis to further elucidate the magnitude and timing of treatment effects, we will seek to create parsimonious models of this outcome as a function of time, treatment arm, stratification factors (center, age, sex, education) and potentially other factors measured at baseline. The primary brain outcome will be a vector measure of fMRI activation in four brain regions of interest, as described above and in previous work from SYNAPSE (7). This measure is also likely to exhibit substantial between-subject variability. We will again analyze the outcome variable in a mixed model, evaluating the treatment effect by estimating a time-by-treatment interaction, and conduct a secondary analysis where we model activation in the four regions as functions of time, treatment arm, stratification factors (center, age, sex, education) and potentially other factors measured at baseline.

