### **Mid-Intervention Cognitive Behavioral Battery: (Weeks 8-9)**

Mid-way through the intervention period, participants will be asked to complete the cognitive battery again (found in full in Appendix A). This will help with statistical analysis, specifically growth curve analysis.

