### Analyses of Secondary Outcomes.

*Dose-response.* We anticipate that there will be a dose-response relationship, with the control arms having the lowest values, high-engagement arms, the highest values, and moderate-engagement arms having values in between. We will construct mixed models to estimate the sizes of these effects, and to determine whether effects are linear or nonlinear in the degree of engagement.

*Subgroup Analyses.* We will conduct a number of analyses aimed at estimating treatment effects within strata of age (younger or older than age 72), gender (male or female), education (greater or less than 14 years), and center (Dallas or Hamburg). We expect each of these strata to comprise roughly half of the subjects, except that our sample will likely be 65% female, reflecting the sex imbalance in the elderly. We will replicate our main analyses in each of the stratum subgroups, and additionally test for interactions.

*Incomplete data.* A major concern in any follow-up study is that there will be substantial dropout, eroding trial power. As indicated above, we expect no more than 15% to 20% of subjects to fail to complete the followup evaluation schedule. This is not a large fraction of dropout, and we have provided for its effects on power in our sample-size calculations. A second concern is that dropouts may differ systematically from completers, potentially introducing bias into estimated treatment contrasts. Our primary approach to analysis is to use mixed models, which give correct results as long as the dropout mechanism is missing at random — i.e., the probability of dropout, given the potentially missing observation and all prior observed data, does not depend on the potentially missing observation. Moreover, as long as the dropout is roughly balanced between treatment arms, it is unlikely to have a substantial biasing effect on estimated treatment effects, even if the dropout mechanism is not missing at random. In any event, if dropout is excessive or is unbalanced between arms, or there is concern that it is not missing at random, we are prepared to conduct analyses for sensitivity to nonignorable (i.e., biasing) dropout using general methods that [name] has developed.

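### The SAP does not settle which model is primary for the memory composite, and its missing-at-random claim does not cover the baseline-plus-post-test ANCOVA if dropout depends on the mid-test differently by arm

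*Combined protocol and SAP*

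**What the plan says.** In the SAP, Analysis of Primary Outcome Variables, the memory composite is handled in three steps.

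- The named primary method: "in primary analyses we will adjust for baseline levels by analysis of covariance", that is, "including baseline values together with treatment arm in a regression model for the post-treatment outcome". The mid-test is not a term in this model.
- A permitted substitute: "Alternatively (and equivalently), we can analyze the outcome variable in a mixed model, evaluating a treatment effect by estimating a time-by-treatment interaction". Its time points are not listed.
- A further model: "We will moreover conduct mixed-model analyses including the intermediate (6-week, mid-treatment) and long-term (1-year) values of the cognitive outcomes", together with the end-of-treatment score. It is called neither primary nor secondary. The sentence after it is the first to be labelled secondary.

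The Incomplete data paragraph, under Analyses of Secondary Outcomes, says: "Our primary approach to analysis is to use mixed models, which give correct results as long as the dropout mechanism is missing at random". It defines that condition as the probability of dropout which, "given the potentially missing observation and all prior observed data, does not depend on the potentially missing observation". On the amount of dropout it says "we expect no more than 15% to 20% of subjects to fail to complete the followup evaluation schedule". It adds that roughly balanced dropout is unlikely to cause much bias, and it offers sensitivity analyses if dropout is excessive, unbalanced or suspected of being nonignorable.

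The mid-test itself is scheduled. In weeks 8-9, "participants will be asked to complete the cognitive battery again" (protocol, Mid-Intervention Cognitive Behavioral Battery).

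**The concern.** The two SAP paragraphs point to different primary analyses, and the choice decides whether the missing-data argument applies. For someone who leaves after weeks 8-9, the earlier observed data include the mid-test score. A likelihood model containing that score is protected when leaving depends on it. An ANCOVA of post-test on baseline and arm is not, because it neither includes the person nor conditions on the score.

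Such dropout is conceivable here. The arms differ in load: on-site classes and project hours at two speeds, against activities at home (protocol, Intervention). The protocol's Potential Risks section notes that participants may be distressed by test performance they see as unsatisfactory. The documents give no data on whether this leads people to leave, or whether it would do so differently by arm.

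At stake is an avoidable bias in the main estimate of a study meant to inform a full trial, when the data that would remove it are already being collected.

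**Working it through.** **What can be reproduced.** 3 arms × 30 = 90. The SAP refers to sample-size calculations, but the text supplied gives no effect size, SD, correlation, alpha or power, so nothing further can be reproduced.

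**People affected, at the SAP's upper figures.**

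- 15%: 0.15 × 90 = 13.5 lost and 76.5 complete, or 25.5 per arm (4.5 lost per arm).
- 20%: 0.20 × 90 = 18 lost and 72 complete, or 24 per arm (6 lost per arm).
- Only those who leave between mid-test and post-test matter here. If that is half of them, it is 2.25 to 3 per arm.

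**Why the ANCOVA can be biased.** Let γ be the coefficient of the mid-test when post-test is regressed on arm, baseline and mid-test. Let δ be the arm coefficient when mid-test is regressed on arm and baseline. By the omitted-variable identity:

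ANCOVA bias = γ × (δ among completers − δ among everyone)

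with, on the SD scale, γ = (r_mid,post − r_base,mid × r_base,post) / (1 − r_base,mid²).

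The bracket is zero if dropout is random or depends only on baseline. It is essentially zero if dropout depends on the mid-test equally in both arms, because the shifts cancel. It is not zero if the dependence differs by arm, even at equal dropout rates.

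**Example.** Assume correlations baseline–mid .70, baseline–post .65 and mid–post .75. Assume a true effect of 0.20 SD at mid-test and 0.40 SD at post-test, 30 per arm, and 20% dropout, all after the mid-test. In one arm the log-odds of leaving fall by 1.5 per SD of mid-test score.

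- γ = (0.75 − 0.70 × 0.65) / (1 − 0.49) = 0.295 / 0.51 = 0.578.
- Simulated ANCOVA bias is +0.066, so the bracket is 0.066 / 0.578 = 0.114 SD.
- Bias relative to the SD of the estimate is 0.066 / 0.221 = 0.30; relative to the effect it is 0.066 / 0.40 = 17%.
- With the mid-test in the model, bias is −0.005 (SD of estimate 0.217).

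**Range of results for one pairwise contrast.** Every input below is assumed except the 15–20% dropout.

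*Set A.* Correlations .60/.55/.70, .70/.65/.75 and .80/.75/.85 (baseline–mid, baseline–post, mid–post). Dropout 15–20% in each arm, half or all of it after the mid-test. Log-odds slope 1 to 1.5 per SD.

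- Dependence in one arm only: ANCOVA bias about 0.02–0.09 SD.
- Opposite dependence in the two arms: about 0.04–0.18 SD.
- Mid-test in the model: about 0.01 or less in absolute value.

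*Set B.* Equal correlations of .5, .7 or .85, or autoregressive .7. Effects 0.25 at mid-test and 0.50 at post-test. Slope 1, all dropout after the mid-test. ANCOVA bias was 0.02–0.06 SD (one arm) and 0.04–0.13 SD (opposite). With the mid-test it was within ±0.004 throughout. Detail at equal correlation .7 and 20% dropout:

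| Dropout depends on | ANCOVA | Baseline + post mixed model | With mid-test |
|---|---|---|---|
| nothing | −0.001 | 0.000 | −0.001 |
| baseline | 0.001 | 0.001 | 0.000 |
| mid-test, same in both arms | −0.001 | −0.001 | −0.001 |
| mid-test, one arm only | 0.037 | 0.037 | −0.001 |
| mid-test, opposite by arm | 0.078 | 0.077 | 0.001 |

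The signs are positive because low scorers were made to leave the intervention arm; the reverse pattern would give a negative bias.

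**Precision.** At 20% random dropout the standard error falls from 0.213 to 0.209 (1.9%) at equal correlation .7, and from 0.258 to 0.246 (4.7%) under autoregressive .7. At equal correlation .5 it falls from 0.253 to 0.250 (1.2%).

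**The case against.** The case on the other side is substantial.

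- **A reader might infer that the primary analysis is settled as a two-time-point model.** The documents do not support that. The Incomplete data paragraph calls mixed models the primary approach, and the model with the mid-test sits under the primary-outcome heading without a rank. That the substitute mixed model uses only baseline and post-test is an inference from its being called equivalent to the ANCOVA. This stands: the defect is an unresolved conflict.
- **The missing-at-random sentence is attached to mixed models and never mentions ANCOVA.** As a statement about a model containing the mid-test, it is right. What fails is carrying it over to the method named for the primary analyses.
- **A reader might infer that leavers add nothing, or that validity always needs the mid-test.** The first is exact for the ANCOVA only; in a two-time-point mixed model leavers still contribute a baseline score. The second is too strong, as the zero-bias rows show.
- **The effect is modest.** In the worked example, root-mean-square error is √(0.066² + 0.221²) = 0.231 against √(0.005² + 0.217²) = 0.217, about 6% larger. A 95% interval would still cover about 94% (normal approximation).
- **The numbers affected may be smaller.** The 15–20% is an upper figure for completing a follow-up schedule that, in the SAP, includes a 1-year value. It need not mean loss before post-test.
- **The plan has safeguards.** They need not respond here. Dropout can be within the expected rate, balanced between arms and missing at random by the SAP's own definition, and still bias the ANCOVA.

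**Conclusion.** The point holds in a limited form. The SAP leaves open which model is primary for the memory composite, and its missing-data assurance fits only one of the candidates. If the ANCOVA is primary, dropout that depends on the mid-test differently by arm biases the contrast by about 0.02–0.09 SD (one arm) or 0.04–0.18 SD (opposite). Against an assumed effect of 0.40 SD that is 0.02/0.40 = 5% to 0.09/0.40 = 22%, or 0.04/0.40 = 10% to 0.18/0.40 = 45%. The two-time-point mixed model shares the bias.

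These sizes rest on assumed correlations, slopes and dropout timing, with all dropout after the mid-test as the extreme case. The documents do not show that such dropout will occur, so they do not support a claim that the primary result will be biased. Precision is a minor reason to change. The reason to act is that the remedy is cheap and matches the approach the Incomplete data paragraph already describes.

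**What to change.** In the SAP, Analysis of Primary Outcome Variables, name one primary estimator for the memory composite: a mixed model for the baseline, mid-test and post-test scores, with categorical time, arm-by-time terms, unstructured within-subject covariance and a small-sample degrees-of-freedom correction. Take the arm contrast at post-test as the primary estimate and include everyone with a baseline score. Keep the baseline-plus-post-test ANCOVA as a supportive analysis, and stop describing the alternatives as interchangeable. In the Incomplete data paragraph, tie the missing-at-random statement to this model.

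This is a change of wording, with no new data collection. It is not quite a relabelling of something already planned: the further mixed model in the SAP also includes a 1-year value, whereas the protocol's schedule ends with post-testing in weeks 15-16. The primary model should therefore list its three visits explicitly.

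The costs are a few more covariance parameters at about 30 per arm, and no help for people who leave before the mid-test.

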We propose a study that would allow us to evaluate the effectiveness of engagement on cognitive function and determine whether mental effort is a contributing factor to changes in cognitive function. We plan to enroll 90 participants in the Impact of Challenging Engagement study and assign them to one of three groups: high-demand photography, moderate-demand photography, and active placebo. These initial groups will allow us to collect data and address the feasibility for converting the project into a full trial. Participants will engage in their different engagement conditions for 15 hours per week, based on successful results from the initial AIM study. In the Impact of Challenging Engagement study, we expect to expand on the results of the AIM study to determine if high-demand activities result in any observable brain changes when compared to moderate demand or placebo activities. Behavioral and neural measures of cognitive change will be assessed, providing considerable insight into mechanisms of change. Subjects will be characterized thoroughly in terms of behavioral tests of cognitive function, and a subset of subjects who meet neuroimaging criteria will undergo an fMRI procedure.

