*Latent Factor Modeling.* As a further form of secondary analysis, we will analyze the cognitive outcome variables simultaneously using a latent-variable approach. With this method, one models the several cognitive variables at each measurement time as being statistically independent given an unobserved, subject-specific latent variable. One accommodates serial correlation within subjects by estimating correlation of the latent variable within subjects over time. The approach evaluates treatment and time effects by modeling the mean of the latent variable as a function of the predictors, and each subject's estimated latent trajectory serves as a summary of his outcome status. We will also apply such models to the four-variate fMRI primary outcome.

*Neuroimaging Analyses.* We will test for a Group x Time interaction on the primary measure of modulation capacity. For the large-scale brain network analyses, we will utilize measures of connectivity between major nodes within the networks as indicators to develop constructs for the executive fronto-parietal network, salience network, and default network at each interval of data collection. To measure increases in hippocampal volume, we will segment the left and right hippocampus into four regions of interest (subiculum, CA1 and CA2/CA3/CA4, dentate gyrus, and entorhinal cortex) for all individual high-resolution MRI images. This division into 4 regions of interest (ROI) will ensure sufficient reliability and reproducibility of the subfield distinctions. These ROIs will be entered into the same Group x Time ANOVA as in the fMRI analyses.

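### The SAP calls a time-by-treatment mixed model equivalent to the primary ANCOVA of the memory composite; as written it is a different and less precise test

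*Combined protocol and SAP*

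**What the plan says.** In the Statistical Analysis Plan, under Analysis of Primary Outcome Variables, "The primary cognitive outcome endpoint will be a composite, scalar episodic memory score". The analysis is then fixed: "in primary analyses we will adjust for baseline levels by analysis of covariance", which the SAP explains as a regression of the post-treatment score on baseline and arm. The next sentence opens a second route: "Alternatively (and equivalently), we can analyze the outcome variable in a mixed model, evaluating a treatment effect by estimating a time-by-treatment interaction". For that mixed model the SAP gives no list of fixed effects, no covariance structure, no baseline covariate and no constraint that the arms share a baseline mean.

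Three other places bear on how to read it:

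- The same paragraph turns to the fMRI outcome with "We will again analyze the outcome variable in a mixed model", evaluated by the same kind of interaction.
- Neuroimaging Analyses, on the hippocampal regions, says "These ROIs will be entered into the same Group x Time ANOVA as in the fMRI analyses".
- Incomplete data, under Analyses of Secondary Outcomes, says "Our primary approach to analysis is to use mixed models". This is not reconciled with ANCOVA as the primary analysis.

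**The concern.** A mixed model with arm, time and their interaction, and with baseline means free to differ by arm, does not adjust for baseline in the way ANCOVA does. On complete two-visit data its interaction is the change-score contrast. The SAP's stated reason for ANCOVA is that baseline scores predict follow-up scores. The permitted substitute uses that information less efficiently, and the text says that nothing changes.

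Two things are at stake. One is precision in a trial with 30 per arm. The other is that two tests, which will sometimes fall on opposite sides of 5%, could each be presented afterwards as the primary cognitive analysis.

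**Working it through.** **Inputs.** From the documents: three arms of 30 (Concise Summary of Project), and at most 15% to 20% of subjects not completing follow-up (Incomplete data). The supplied text gives no r, SD, effect size, alpha or power, so there is no figure of the plan's own to reproduce. Assumed: r from 0.5 to 0.9, SD 1 at both visits, two-sided 5%, bivariate normal scores.

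**Step 1: what each model estimates.** Let B and Y be the differences between two arms in mean baseline and mean post-test score.

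- Interaction with free baseline means: Y − B.
- ANCOVA: Y − bB, with b estimated (about r when SDs are equal).
- Interaction with baseline means constrained equal: the same as ANCOVA on complete two-visit data.

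In 120 simulated two-arm trials fitted by maximum likelihood, the free-baseline interaction matched the difference in mean change to within 6e-8. The common-baseline version matched ANCOVA to within 7e-8. So the claim of equivalence is true for one form of mixed model and false for the other.

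**Step 2: variance of a pairwise contrast, n per arm, large samples.**

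- ANCOVA: (1 − r²) × 2/n
- Free-baseline interaction: 2(1 − r) × 2/n
- Ratio: 2(1 − r)/(1 − r²) = 2/(1 + r)

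At r = 0.7 and n = 30 the standard errors are √(0.51 × 2/30) = 0.184 and √(0.60 × 2/30) = 0.200. The ratio is 2/1.7 = 1.18.

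**Step 3: power and agreement for one pairwise contrast.** Two-arm simulation, 30 per arm, complete data, 200,000 replicates per cell, with the effect set so that ANCOVA has 80% power.

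| r | 0.5 | 0.6 | 0.7 | 0.8 | 0.9 |
|---|---|---|---|---|---|
| Variance ratio, 2/(1 + r) | 1.33 | 1.25 | 1.18 | 1.11 | 1.05 |
| Variance ratio, simulated | 1.31 | 1.23 | 1.16 | 1.09 | 1.03 |
| Effect (SD) for 80% ANCOVA power | 0.64 | 0.59 | 0.53 | 0.45 | 0.32 |
| Interaction power | 69% | 72% | 74% | 77% | 79% |
| Tests disagree on p < 0.05 | 16% | 13% | 11% | 8% | 5% |
| Per arm for interaction to match ANCOVA at 30 | 39 | 37 | 35 | 33 | 31 |
| Null: either test significant | 7.2% | 7.1% | 6.9% | 6.5% | 6.1% |

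The simulated ratio is a little below the formula because ANCOVA pays for estimating its slope. The matching sample size is 30 times the simulated ratio, for example 30 × 1.31 = 39. Under the null each test alone rejects in 4.9% to 5.1% of trials.

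**Step 4: three-arm F test.** Means 0, d/2 and d, with ANCOVA at 80% power, for r = 0.5, 0.7, 0.9:

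- Interaction power: 68%, 73%, 78%.
- Disagreement: 17%, 12%, 6%.
- Null, either significant: 7.4%, 6.9%, 6.0%.

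**Step 5: 20% dropout.** Let m of n subjects per arm have a post-test, and let the mixed model keep those with a baseline only. The interaction variance per arm is (1 − r²)/m + (1 − r)²/n, against (1 − r²)/m for ANCOVA on completers. The ratio is 1 + (m/n)(1 − r)/(1 + r). With m/n = 0.8 it is 1.27, 1.14, 1.09 and 1.04 at r = 0.5, 0.7, 0.8 and 0.9. It exceeds 1 for every r below 1.

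**The case against.** The strongest objection is that the SAP does not write the mixed model out. A standard version with a common baseline mean would make the statement correct for complete two-visit data. The wording that points the other way concerns imaging outcomes, and the sentence on the primary approach sits in a paragraph about missing data and may describe the plan in general. This stands as a limit on certainty: the ordinary reading is supported but not proved. It does not remove the point, because under either reading the SAP has to say which model it means.

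Second, mixed models gain from incomplete data. A free-baseline model that also uses the mid-test, with all 20% dropping out after that visit, can be compared with ANCOVA on completers. The variance ratios at r = 0.5, 0.6, 0.7, 0.8, 0.9 are then 1.24, 1.17, 1.11, 1.05, 1.00 with equal correlations between visits, and 1.20, 1.13, 1.06, 1.00, 0.95 with serially decaying ones. So the loss can vanish or reverse at high r. However, the SAP introduces the model with the mid-test as a further analysis, not as the one it calls equivalent. The gain comes from the extra data, and a baseline-adjusted mixed model can use the same data.

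Third, the error rates of 6% to 7% need someone to report the better of two results. The plan does not propose this, so they show what the open choice would allow and do not predict conduct.

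Fourth, the size is modest: at r of 0.8 to 0.9 the loss is 1 to 3 power points. The Purpose section also says the data are meant to "address the feasibility for converting the project into a full trial". Both are fair and bear on severity.

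Fifth, the Intervention section describes pseudo-random assignment that depends partly on the study's needs, so the statement that both estimators are unbiased is conditional on effective randomisation. If arms differ systematically at baseline, the two estimates can differ by more than chance, which makes naming one of them more important.

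**Conclusion.** The concern holds. As written, the SAP treats as interchangeable two analyses that coincide only under a common-baseline constraint it does not state. Under randomisation this is a matter of precision and of an open choice of primary test, not of bias. For a pairwise contrast with complete data the cost is about 11 power points at r = 0.5, 6 at r = 0.7 and 1 at r = 0.9. These figures rest on an assumed r, equal SDs and the ordinary reading of the mixed model. It should be fixed, given how little that takes, but it does not threaten the trial.

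**What to change.** In Analysis of Primary Outcome Variables, delete the parenthetical claim of equivalence and name one primary analysis of the memory composite. Either of these would serve:

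- ANCOVA of the post-test score on baseline and arm. It is simple, but it drops participants who have a mid-test and no post-test.
- One mixed model of the mid- and post-test scores, with baseline as a covariate whose effect may differ by visit, and the arm contrast at post-test as the primary estimate. It keeps those participants and fits better with the missing-at-random argument under Incomplete data. The mid-test is already scheduled: under Mid-Intervention Cognitive Behavioral Battery, "participants will be asked to complete the cognitive battery again".

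List the unadjusted time-by-treatment interaction as a sensitivity analysis. If a common-baseline mixed model was intended, state the constraint and the fixed effects. Then bring the Incomplete data sentence on the primary approach into line with the choice.

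The cost is a few sentences in the SAP. R and SAS, the packages it names, fit all of these models. Visits, data collected and sample size do not change.
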